8.2 Equipment

Component description	Name
Mobility+ device	Mobility+ Enteral Feeding System
ENFit Syringe.	Reusable, 60ml ENFit syringe
Generic cross body bags to wear Mobility+ in	Off the shelf brand

8.3 Participants

This is a first in human post-market clinical study to evaluate the Mobility+ system, being carried out following market approval (i.e., FDA clearance). 25 participants will be enrolled to ensure data can be obtained for 20 participants (the expected drop-out rate is estimated at ~20%), as this is considered appropriate for a post-market clinical study on a low-risk device and will add meaningful data to device risk management files. If more than 5 participants drop out, re-recruitment will aim to bring the sample size up to 20.

Recruitment will aim to obtain a mix of female and male participants who meet the inclusion criteria. Screening questions will be used by operators during the recruitment process to ensure participants are eligible (See **Appendix 1** and **Appendix 2**).

8.4 Inclusion and Exclusion Criteria

Inclusion criteria	
Participants with Gastrostomy (G) tube or Jejunostomy (J) tubesParticipant must require enteral tube feeding every day, as determined at the time of study enrolmentParticipant must use commercially available enteral formula with standard enteral feeding system(s) (gravity bag, bolus, pump or combination(s)), for some or all of their tube feeds, for daytime or day and night-time feedingParticipant must be EN dependent i.e., 500 ml minimum daily feed intake from ENParticipants must be able to swap from current system to Mobility+ for a minimum of two daily feeds per day for duration of study (Study days 1 -14)Participant must be ≥ 18 to reflect the subset of the intended use population being evaluatedParticipant must be willing to participate in the study and provide consent).Participants must have been on an enteral feeding regime for a minimum of 10 weeksParticipants clinical functional capacity is adequate as determined by operator clinical judgement, to enable them to participate fully in the studyParticipants are suitable candidates for using Mobility+ as determined by operator clinical judgement on participant enteral feeding needs (as per prescription) and alignment with Mobility+ Flow Rate Guide (see Giving Set SKU decision tree for prescribing Mobility+ Figure 6)
Exclusion Criteria	
Participants who do not use commercially available enteral formula for some or all their formula needsParticipants unable/unwilling to provide consentParticipants whose enteral feeding needs do not match the offering of the Mobility+, as determined by operator clinical judgement (see Decision Tree for prescribing Mobility+ Figure 6)

	4. Participants who have inadequate clinical functional capacity, as determined by operator clinical judgement to participate fully in the study e.g. neuromuscular or neurodegenerative disorders, or developmental delay. 5. Participants with very limited mobility, as determined by operator clinical opinion
--	---

Note: In considering functional capacity, the operator will consider the ability to conduct critical tasks associated with successful use of Mobility+ (i.e. removal of protective caps; connecting filling set to pouch in correct orientation; operating clamps; orientating 3-way valve; pushing syringes of feed into pouch; disconnecting tubing (filling and giving sets); connecting giving set to extension set or feeding tube; wearing Mobility+ and coiled tubing on the body; Sit, walk, and stand while wearing Mobility+)

8.5 Study Measurements

The study measurements which will be taken are detailed in Table 3 below:

Table 3: Study measurements

Baseline measurements:	
 Demographics (Appendix 3) Average volume and Kcals of feed consumed / day (Appendix 3) Quality of life measure (Appendix 5) Participant perspectives on mobility, ease of use (current system(s)) and feeding intolerance symptoms (Appendix 4)
Trial days	
 Tubing SKU check (Appendix 6)
Interim survey questions (Study Day 7)	
 Tubing SKU check, safety and effectiveness check, compliance and calorie intake check (Appendix 8)
End of study measurements (Study Day 14):	
 Quality of life question (Appendix 7) Participant perspectives on mobility and ease of use of Mobility+ system (Appendix 7) Note of tubing SKU used, safety and effectiveness check, compliance and calorie intake check, General end of study questions (wearing, wellbeing, future use etc.) (Appendix 7)

8.6 Compliance

[figure not shown]
Phone communication surveys on Study days 7 and 14 will collect information on the amount participants are using, to capture if they are using Mobility+ for a minimum of 2 daily feeds (Appendix 8).

Note: In some cases, participants may not comply fully with their enteral feeding regime due to issues unrelated to the study or feeding system. At screening, potential participants will be asked how often they skip or cut-short feeding sessions to determine if general compliance with enteral nutrition (EN) feeding may be an issue. Questions on compliance will also be asked on Study Days 7 and Day 14 (See Appendix 8). Poor compliance (participants who take less than two daily feeds using Mobility+), should it occur, will be reported in the study results and sub analyses will be conducted on participants who met the criteria.

8.7 Selection of giving set tubing SKUs

During **eligibility screening**, patient e-medical records will be reviewed to allow operators to determine if the Mobility+ system is suitable for potential participants based on the enteral nutrition formula the person uses, their **estimated** flow rate needs (mls/hour), and the information in the Mobility+ Flow Rate Guide (FRG) on indicative flow rates achieved with various formula and tubing SKU combinations. *Note: The process of healthcare professionals using the FRG to allow selection of an appropriate tubing SKU is validated by expert review.*

Operators will use FRG and the potential participant's enteral feeding regimen prescription to estimate which giving –set tubing SKU (from four available options) best suits the participant's needs, with the approach being to pick the SKU which will provide a flow rate that is slightly slower than the participant's estimated flow rate. The operator will refer to the Decision Tree for Prescribing Mobility+ (see **Figure 6**) when deciding if the potential participant should be invited for a clinic visit.

- Decision Tree Questions
- Giving Set SKU suitable for patient
- No Giving Set SKU suitable for patient

Figure 6: Decision Tree for prescribing Mobility+

During the clinic visit, the operator will administer the screening questionnaire (**Appendix 2**) which will allow the operator to gauge the participant's **calculated average flow rate**. The operator will then use the participant's calculated average flow rate, the FRG and Decision Tree for Prescribing Mobility+ (see **Figure 6**) to make a final decision on which giving set SKU the participant will begin the trial period with. As per the Decision Tree for Prescribing Mobility+, the operator will prescribe the giving set SKU which provides a flow rate slower than the participant's calculated average flow rate and exercise caution when prescribing the 1900mm for use in the trial. This reduces the likelihood of the participant starting the trial with flow rates that are too high, and reduces the risks associated with this e.g. nausea and vomiting, among others. The trial period will allow time for an assessment on whether this initially selected tubing SKU is the best-fit for the participant to continue to use for the study days.

Participants will be made aware at enrollment that operators who are licensed to prescribe enteral feeding systems may advise changes to the giving-set tubing SKU they use, throughout the study, should clinical and participant factors necessitate this.

During phone communications in the trial period days, the operator will advise the participant about what, if any, changes to make to the tubing SKU they are using, which will be logged (**Appendix 6**). If necessary, participants will be advised by the operator to move to tubing SKUs which provide faster or slower flow rates as tolerated (See Phone Communication Decision Tree Figure 7), until the participant has their optimum tubing SKU selected by the end of the trial period, for use during the study days. The participant will then ideally continue with the selected tubing SKU for the duration of the study days.

[figure not shown]

Figure 7: Phone Communication Decision Tree

However, on study Day 7 operators will discuss the tubing SKU being used with the participant and advise if any changes need to be made. Any changes made to the SKU being used will be logged by the operator (**Appendix 6**). On study day 14 (at outcome), operators will log the SKU that participants finished the trial with.

Participants will be supplied with devices, tubing SKUs and other consumables necessary, for trial period and study days.

Table 4 and **Figure 8** below summarizes the study schedule and the subsequent text details what occurs at screening and baseline visit, and in the pre-intervention and intervention phases.

Note: Operators will, if applicable, log reports on 1) surveys/phone communications that subjects fail to respond to (including reasons), and 2) participants withdrawn (including reason for withdrawal)

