3.0 Purpose

The purpose is to evaluate the safety and effectiveness of Mobility+ enteral feeding system via this initial post-market study (510k clearance number K222678) in adults, a subset of the intended use population. This evaluation will be conducted in a prospective, single arm, non-randomized clinical study.

Hypothesis and Objectives

The study hypothesis is that Mobility+ meets its intended use, safely. The objectives are to evaluate the below primary and secondary endpoints, through execution of this protocol:

Endpoint	Detail	How it will be measured
Primary: Safety and Effectiveness of Mobility+	Evaluate participants who have received familiarization training can use device, according to IFU, to allow delivery of liquid nutrition to their feeding tube, in a real-life setting (home), safely (i.e. can execute critical device use tasks to allow feeding, without serious adverse events) and with effectiveness (i.e. using Mobility+ for the majority or all of their feeding sessions i.e. two daily feeds, minimum)	Phone communication and checklist (Appendix8)

Secondary: Usability of Mobility+	Evaluate Participant perspectives on mobility, ease of use and tolerance, with their current feeding system(s) and Mobility+	Participant perspectives surveys: Baseline (Appendix 4) End of study (Appendix 7)
	Evaluate changes in participant Quality of Life (QoL)	QoL survey at baseline (Appendix 5) and QoL question at end of study (Appendix 7)
	Estimate if participants consume similar average volume (and kcals) of feed/day during the study, compared to baseline	Collect descriptive data on estimated average feed volume and kcals consumed at baseline (Appendix 3) and at end of study (Appendix 8)

The outcome will be presented in a study report.

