8.11 Phone Communication

1. Pre-intervention phase – Trial days

Phone communication on **Trial Days 1; 3 and 5**: Participant is contacted by telephone to ensure the participant is becoming familiar with using the device including the most appropriate giving-set tubing SKU. (**Appendix 6**).

2. Intervention phase – Study days

- Phone communication - Study **Day 7**: Participant is contacted by telephone to ensure they are successfully and safely feeding with an appropriate tubing SKU, and check compliance and calorie intake (**Appendix 8**).
- Phone communication -Study **Day 14**: Participant is contacted by telephone to ensure participant is successfully and safely feeding with an appropriate tubing SKU, and check compliance and calorie intake. Operator also evaluates self-perceived wellbeing, mobility, wearing methods, and longer-term device use wishes (**Appendix 8**) Administer participant perspectives outcome survey, including question on QoL (**Appendix 7**)

Note: Regarding disposal – as per IFU, devices are disposed of alongside normal waste.

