8.13 Monitoring

PI will monitor participants experience of feeding with Mobility+ during the study as per schedule of phone communications in **Table 4** Study Schedule, and as outlined in **Appendices 6 and 9**. Should any adverse events or health threats become known to the operator via phone communications or otherwise, the operator will proceed to assess these as per **Appendices 9 and 10**. Furthermore, participant hospitalization for any reason during the trial days or study days will necessitate the ceasing of a participant's participation in this study (**Appendices 6 and 8**).

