5.0 Statistical test applied

The statistical test used was a paired T-test with ANOVA. Statistical significance was set at $P < 0.05$. Analyses were performed with IBM SPSS Statistics for Windows, version 29.0.1 (IBM Corp., Armonk, N.Y., USA).

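### Usability, symptoms and quality of life are asked after baseline only on Study Day 14, so anyone who leaves earlier drops out of these results, and 2 of the 19 included participants are not accounted for

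*Protocol*

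**What the plan says.** **Timing of the outcome survey.** Protocol 8.11 places it in the Study Day 14 call: "Administer participant perspectives outcome survey, including question on QoL". Table 3 (8.5) and Table 4 (8.8) show the same. Appendix 7 holds the perspectives items, the symptom questions with severity, the quality-of-life question and the question on using the device again. Apart from baseline, none of these is asked at any other time.

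**Withdrawal.** The note at the end of Protocol 8.7 asks operators to log missed surveys and calls with reasons, and "participants withdrawn (including reason for withdrawal"). No survey is attached to withdrawal. Section 8.13 adds a forced exit: "participant hospitalization for any reason during the trial days or study days will necessitate the ceasing of a" participant's part in the study.

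**Numbers.** Protocol 8.3: "25 participants will be enrolled to ensure data can be obtained for 20 participants (the expected drop-out rate is estimated at ~20" per cent). It continues: "If more than 5 participants drop out, re-recruitment will aim to bring the sample size up to 20". SAP 3.0 reports 19 participants included. SAP 6.0 and 7.0 give baseline and outcome data for 17.

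**Analysis.** SAP 5.0: "The statistical test used was a paired T-test with ANOVA". The SAP names no analysis set and no method for missing values.

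**What is also collected earlier.** For Study Day 7, Table 3 lists a "safety and effectiveness check, compliance and calorie intake check (Appendix 8"). The intake objective in Protocol 3.0 is descriptive: "Collect descriptive data on estimated average feed volume and kcals consumed at baseline" and again at end of study. Table 4 also marks an intake estimate on Study Day 7.

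**The concern.** A before-after comparison needs both values. A participant who leaves before Study Day 14 has a baseline score but no outcome score, so the paired test omits that person even after days or weeks on the device. The wish to use the device again has no baseline value; it is simply unknown for leavers. Re-recruitment under 8.3 restores the head count but not the leavers' answers.

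The loss need not be neutral. The protocol itself foresees device-related difficulties: 8.10 gives reflux and long feeding times as reasons for changing tubing, and the Study Day 7 sheet lists intolerance, abdominal discomfort and slow feeding. If some participants leave because such problems persist, their missing ratings would tend to be the less favourable ones. In a single-arm study no comparator shares this loss, so any selection passes straight into the reported mean change.

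**Working it through.** **1. Planned numbers (Protocol 8.3).** Target with data 20, dropout about 20%: 20 / (1 − 0.20) = 25. This reproduces the planned enrolment and implies 25 − 20 = 5 leavers. The sample-size arithmetic is not at fault.

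**2. Reported numbers (SAP 3.0, 6.0, 7.0).** 548 − 493 − 11 − 25 = 19, as stated. 19 − 17 = 2 not reported; 2/19 = 10.5%. The baseline table is also limited to 17, so a reader cannot tell whether the other two ever used the device.

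**3. What remains for a leaver.**
- Leaves in the trial days: tubing checks with reasons for change from the calls reached (Appendix 6), any adverse event record, and the withdrawal reason.
- Leaves after the Study Day 7 call: also the Day 7 answers on safe and successful feeding, number of feeds, volume and tubing (Appendix 8).
- Takes fewer than two daily feeds but stays in: kept and reported under 8.6, and still due the Day 14 survey.

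Neither Appendix 6 nor Appendix 8 contains the perspectives, quality-of-life or symptom-severity items. Those results are fully affected; intake and the safety and effectiveness check are only partly affected.

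**4. Effect on a mean change.** Mean over all = (completers × completer gain + missing × change in the missing) / total. The gains and changes are assumptions, on the 1 to 5 item scale of SAP 4.0.

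| Completers + missing | Completer gain | Missing had no change | Missing lost 1 point |
|---|---|---|---|
| 20 + 5 (plan) | 0.5 | 10/25 = 0.40 | (10 − 5)/25 = 0.20 |
| 17 + 2 (SAP) | 0.5 | 8.5/19 = 0.45 | (8.5 − 2)/19 = 0.34 |
| 20 + 5 (plan) | 1.0 | 20/25 = 0.80 | (20 − 5)/25 = 0.60 |
| 17 + 2 (SAP) | 1.0 | 17/19 = 0.89 | (17 − 2)/19 = 0.79 |

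**5. Effect on the paired test.** Assumed: completer gain D = 0.8, SD of change s = 1.0, two-sided (the SAP states neither an SD nor sidedness). Completers alone: t = D / (s/√n). With the missing added at change c and overall mean m, the sum of squares is (n_c − 1)s² + n_c(D − m)² + n_m(c − m)², where n_c and n_m count completers and missing.
- 17 completers: t = 0.8 × √17 = 3.30, p = 0.0045. Adding 2 with no change: p = 0.005. Adding 2 with a 1-point loss: p = 0.026.
- 20 completers: t = 0.8 × √20 = 3.58, p = 0.002. Adding 5 with no change: p = 0.0025. Adding 5 with a 1-point loss: p = 0.069.
- Range for 17 + 2 with a 1-point loss, SD 1.0: at gain 0.6, p goes from 0.025 to 0.096; at gain 1.0, from 0.0008 to 0.007.

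**The case against.** The strongest reply is that leavers are not without data, and that leaving need not reflect the device.

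- **Other records exist.** Step 3 of the working shows what remains. This stands, and limits the point to the Appendix 7 items. A reader might infer that a leaver is absent from every before-after comparison. That goes too far: someone who leaves after the Study Day 7 call has an on-device intake value, although Protocol 3.0 names end of study as the comparison point.
- **Using the device little is not leaving the study.** Section 8.6 retains low users. This stands; the gap concerns withdrawals only.
- **The cause of leaving is unknown.** Section 8.3 gives no reasons behind its 20%. Section 8.13 removes anyone hospitalised for any cause, and 13 of the 17 reported participants have malignancy (SAP 6.0), so exits unrelated to the device are plausible. This stands: the direction of bias is a risk, not a finding.
- **Five device users lost is an upper figure.** Section 8.10 lists enrolment before the questionnaire that confirms eligibility, so some of the five may never use the device. With the SAP's gap of 2 in 19, the shift is roughly half as large.
- **Early answers measure something else.** Section 8.1 treats the trial days as familiarisation and 14 days as the time needed to assess the device. This stands against putting stop-time answers into the main comparison, but not against collecting them.
- **These are secondary endpoints without a success threshold, and symptoms carry no score in the SAP.** Both are true. The arithmetic on means applies to the scored perspectives and quality-of-life items; for symptoms the loss is simply of the outcome answer.

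**Conclusion.** The point holds in a limited form. The plan, followed exactly, gives completer-only results for perspectives, symptoms, quality of life and the wish to use the device again, with no means of judging whether leavers differed. On assumed values, a 0.5-point completer gain overstates the mean over all participants by 0.1 to 0.3 points at the planned loss of 5 in 25, and by about 0.05 to 0.16 at the SAP's 2 in 19. Under the assumptions in step 5, a 1-point loss among the missing takes p above 0.05 at the planned loss but not at 2 in 19, unless the completer gain is nearer 0.6.

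Two stronger readings are not supported. A reader might infer that the two unreported participants stopped because the device did not suit them, and restate the 17 of 17 who fed safely and successfully as 17/19 = 89.5%. The SAP gives no reason for their absence, so that figure is only a worst case. Nor do the documents show that the reported gains are biased; they show that bias could not be detected.

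This should be corrected. It affects how the secondary results can be read, and the remedy is small.

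**What to change.** **Collection (Protocol 8.7 and 8.11).** At the contact where withdrawal is recorded, the operator asks the Appendix 7 items by phone of anyone who has used the device. The form cannot be used unchanged, because it refers to the last 14 days or two weeks; the recall wording should cover the time since the participant started using Mobility+.

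**Analysis (SAP 5.0).** Keep the Day 14 comparison. Beside it, report a sensitivity analysis of all participants who used the device, using stop-time answers where they exist. Where there are none, show a no-change and a 1-point-loss scenario, labelled as assumptions.

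**Accounting (SAP 3.0, 6.0 and 7.0).** State what happened to the 2 of 19: whether they used the device, when they left, and the logged reason.

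**Cost.** One phone questionnaire for about five people at the planned dropout, a minor rewording of an existing form, and one extra table line. The downside is that stop-time answers follow a shorter exposure, possibly before the tubing SKU is settled, so they must be labelled as such. The SAP is written in the past tense, with data already gathered, so the collection change may serve only further enrolment or a later study. The scenario analysis and the accounting can still be done.

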8.8 Study Schedule and Flow

Table 4. Study Schedule

Day	Pre intervention	Intervention Phase (21 consecutive days)													
		Trial Days 1 to 7	Study Day 1	Study Day 2	Study Day 3	Study Day 4	Study Day 5	Study Day 6	Study Day 7	Study Day 8	Study Day 9	Study Day 10	Study Day 11	Study Day 12	Study Day 13
Clinic visit	X														
Phone Communication		X (days 1,3,5)							X						X
Participant info sheet	X														
Screening Questionnaire	X														
Giving Set Tubing Selection	X														
Consent & data privacy, Enrolment	X														
Record Demographics	X														
Familiarization Training	X														
Device First clinical use		X													
Participant perspectives survey	X														X
- QoLmeasure	X														X
Estimate EN intake (kcals & volume)	X								X						X

	Pre intervention	Intervention Phase (21 consecutive days)														
Day	Clinic Visit	Trial Days 1 to 7	Study Day 1	Study Day 2	Study Day 3	Study Day 4	Study Day 5	Study Day 6	Study Day 7	Study Day 8	Study Day 9	Study Day 10	Study Day 11	Study Day 12	Study Day 13	Outcome Study Day 14
Clinic visit	X															
Phone Communication		X (days 1,3,5)							X							X
General End of Study Questions																X

[figure not shown]

Figure 8. Study Flow Chart

8.9 Screening

- Conduct eligibility screening using the eligibility screening log (see **Appendix 1**) and information from patients' electronic medical records. Ensure that the candidate meets the study inclusion criteria. Check if the candidate's enteral nutrition formula is listed on the Mobility+ FRG.
- Develop an understanding of the candidate's flow rate needs. Information on flow rates may be listed in patient electronic medical records or determined based on information such as patient diagnosis, feeding method and type of feeding tube. Where necessary, consult with other study staff (e.g dietitian) to determine a patient's estimated flow rate range and maximum flow rate likely to be tolerated.
- Consult FRG and use the Giving Set SKU decision tree for prescribing Mobility+ (see **Figure 6**) to estimate a suitable giving set SKU for candidates. Note, if the indicative flow rates in the FRG are not suitable for the candidate, they are not eligible for inclusion in the study.
- Assess whether a candidate's mobility and clinical functional capacity are adequate to allow them to participate in the trial.
- Contact eligible candidates by phone and give them a brief description of the clinical trial. Schedule a clinic visit with candidates that are interested in participating in the trial.

